1.0 INTRODUCTION AND STUDY RATIONALE

Glioblastoma is the most common primary malignant type of brain tumor in adults (2). Surgical tumor resection followed by chemoradiation therapy is the standard of care for patients with glioblastoma, but its prognosis is still fairly dismal (median survival time = 15 months) (3, 4). One major concern that prevents effective treatment management is the difficulty of differentiating between pseudo-progression and true-progression (5). Pseudo-progression occurs in about 20-30% of glioblastoma patients typically within 3 months after radiotherapy with or without chemotherapy has been completed (6). Pseudo-progression is a local inflammatory reaction caused by irradiation and enhanced by concurrent chemotherapy, which leads to a transient increase of blood brain barrier (BBB) permeability (7, 8). The BBB, however, is also disrupted by neoplasm (9). Therefore, both pseudo- and true-progressions appear with an increased contrast enhancement in MRI, and there are currently no established techniques to differentiate between them (5). Pseudo-progression is typically known to be associated with better clinical outcomes (10). Thus, as illustrated in Fig. 1, pseudo-progression mistaken for true-progression results in the discontinuation of an effective therapy, while true-progression mistaken for pseudo-progression leads to the continuation of an ineffective therapy that may induce adverse side effects.

[figure not shown]

Fig. 1. Misdiagnosis of glioblastoma progression. Pseudo-progression mistaken for true-progression results in the discontinuation of an effective therapy, while true-progression mistaken for pseudo-progression leads to the continuation of an ineffective therapy.

Dynamic contrast enhanced magnetic resonance imaging (DCE-MRI) has the potential to differentiate between pseudo- and true-progressions in glioblastoma (11-13). The contrast-enhancing lesions of pseudo-progression are due to inflammatory BBB disruption (7, 8), whereas those of true-progression are caused by neoplastic BBB disruption (9). Therefore, true-progression typically presents higher perfusion than pseudo-progression (11-13). Dynamic susceptibility contrast (DSC) MRI is the most common technique for a non-invasive assessment of blood perfusion in the brain (14, 15). However, hemorrhagic changes within the resection cavity after surgery causes susceptibility artifacts, which often interfere with DSC-MRI, leading to false interpretation (16-18). On the other hand, DCE-MRI can assess the blood perfusion with minimal susceptibility artifacts (19-22), thus DCE-MRI may differentiate glioblastoma progression better than DSC-MRI (11).

However, the measurement variability across different MRI scanners remains a serious concern, as it hinders data comparison among institutes to retrieve a reliable threshold for accurate prognosis and subsequent treatment optimization (23). Each MRI vendor provides unique hardware configurations, pulse sequences and reconstruction algorithms, which cause variations in the quantitation of tissue contrast-agent concentration and, consequently, the DCE-MRI parameters (23). An external phantom with a known contrast-agent concentration may allow us to detect and correct the variation. Since the DCE-MRI measurement may drift due to hardware instability (24), it would be ideal if the phantom could be miniaturized to be imaged concurrently in the bore of a standard MRI scanner with a patient for real-time quality assurance.

[figure not shown]

Fig. 2. Point-of-care portable perfusion phantom, P4. (A) Photograph and schematic of the perfusion phantom. This phantom contains two chambers separated by a semi-permeable membrane. Before use, both chambers are filled with degassed/deionized water. After MRI contrast agent is infused to the top chamber (from the left), it diffuses to the bottom chamber through the semi-permeable membrane. (B) DCE-MRI images of the phantom before (baseline) and at 0, 4 and 8 minutes after MRI contrast infusion.

The use of a static phantom comprised of multiple objects with different contrast-agent concentrations was originally suggested to correct the variation in quantitating contrast-agent concentrations of tissues (25). However, a static phantom may not serve as a reliable standard for dynamically changing tissue contrast-agent concentration, because a) the movement of contrast agents in vivo causes additional signal reduction that cannot be replicated by a static phantom, b) the number of data points obtained from a static phantom is small, leading to larger fitting errors, and c) most B₁ mapping techniques are T₁ dependent, thus the nominal flip angle delivered to a static phantom with high contrast-agent concentration cannot be accurately measured, especially in high field MRI (\geq 3T) (26-29). Therefore, a perfusion phantom with a varying contrast-agent concentration is required for accurate correction of MRI system-driven error. A few perfusion phantoms have been developed (30, 31), but these phantoms are too bulky to be simultaneously imaged with a human subject. In addition, these large phantoms are costly and not easily operable by typical MRI technologists, limiting the potential for widespread and routine clinical use. We recently developed a perfusion phantom named P4 (Point-of-care Portable Perfusion Phantom) that significantly reduces variation in quantitating the perfusion of human tissues across different MRI scanners (1). Figure 2A is a photograph of the P4 with its dimensions. is composed of top and bottom chambers with a semi-permeable membrane placed between them. Both chambers are filled with degassed/deionized water before use. After starting DCE-MRI, an MRI contrast agent is infused to the top chamber at a constant rate using a syringe pump. contrast agent displaces the water in the top chamber and diffuses to the bottom chamber as shown Our lab-made software automatically segments the entire region of the bottom chamber (ROI), and the mean value within the ROI is calculated automatically, creating contrast enhancement curves (CEC) as shown in Fig. 2C. The dynamic change of contrast concentration in the bottom chamber was linear for 10 minutes (0.11 mM/min), when independently measured using liquid chromatography-mass spectrometry detection (LC-MS) method (32). repeatability of phantom CEC measured by intra-class correlation coefficient (ICC) (33) was larger than 0.99 in all measurements. Please see our paper for more details (1). The P4 is small enough to be imaged with a human subject and is large enough not to suffer from the partial volume effect, thus MRI system-driven error can be detected during human imaging. correction, the within-subject coefficient of variation (wCV) of the volume transfer constant (Ktrans), a DCE-MRI parameter, was about 20%, but after error correction using the P4, the

variation was reduced to about 4% (1). Figure 3 shows the K^{trans} values averaged in each of the four organ regions of three volunteers (n=12) when two different 3T MRI scanners were used (1). Before correction, the ICC between the two data sets was 0.89, and the ICC was not improved by static phantom based error correction (ICC=0.86). However, after P4-based error correction, ICC was increased to 0.99. The P4 is easily operable by MRI technologists, thus it has great potential to facilitate multi-site clinical trials employing quantitative DCE-MRI (qDCE-MRI). Of note, the clinical utility of the P4 was recently demonstrated (34). After P4-based error correction, the change of K^{trans} in pancreatic tumors favorably responding to chemotherapy was able to be significantly differentiated from that in non-responding tumors (p<0.0001) (34). Besides, the P4 was able to improve the accuracy in risk stratification of prostate cancer when assessed by qDCE-MRI (35).

[figure not shown]

Fig. 3. K^{trans} maps before and after correction. K^{trans} averaged in each of the four organs of three volunteers (n=12), when Scanner-A (Y-axis) or Scanner-B (X-axis) was used. (A) before or (B. C) after correction using (B) the static phantom (SP) or (C) P4 (1).

We now hypothesize that the variability in qDCE-MRI measurement of glioblastoma across different scanners will be significantly reduced when MRI system-driven error is corrected using the P4, leading to better differentiation between pseudo- and true-progressions. **Figure 4A**

shows the Gaussian distribution of the K^{trans} value of glioblastoma with true- or pseudo-progression in Yun *et al*'s study (13), where the area under the receiver operator characteristic curve (AUC) was 0.76. **Figure 4B** shows the hypothetical result when the measurement variation is reduced fivefold by our method as demonstrated in **Fig. 3**, increasing the AUC drastically (0.76 vs 0.99). The goal of the proposed study is to conduct the preliminary test of this hypothesis before validating our methodology in an extended multi-site clinical trial (e.g., R01 or U01 study).

[figure not shown]

Fig. 4. Hypothetical Gaussian distribution of glioblastoma K^{trans} values of pseudo- and true-progression groups (A) before and (B) after P4-based error correction.

2.0 OBJECTIVES

2.1. Primary goal

To determine whether the differentiation between pseudo- and true-progressions of glioblastoma can be improved in quantitative DCE-MRI measurement when the P4 phantom is used for error correction.

2.2. Secondary goal

To determine whether the reproducibility of quantitative DCE-MRI measurement of glioblastoma can be significantly increased when MRI system-driven error is corrected using the P4 phantom.

3.0 INVESTIGATIONAL PLAN

3.1 Study Design

Figure 5 is a flow chart that illustrates our overall study plan. Each patient will be treated with surgery and followed by radiotherapy with or without chemotherapy. Then standard-of-care brain MRI will be applied every 2~3 months. If a newly or enlarged enhancing lesion is observed in one of the standard-of-care MRI and it is uncertain whether it is pseudo or true-progression, a clinical research coordinator will contact the patient for recruitment. All participants will sign an informed consent form that fully discloses the investigational nature of this study before enrollment. If the patient agrees to participate in this study, a clinical research coordinator will schedule two imaging sessions with the P4 within a one-week period, assuming that the glioblastoma perfusion parameters will not change over a week. The second imaging test will be scheduled at least 24 hours after the first one. Pseudo or true progression of glioblastoma will be determined via histopathologic analysis after biopsy (or surgery) or via the Response Assessment in Neuro-Oncology (RANO) criteria (6). In this pilot study, a

Fig. 5. Overall study plan (TMZ=temozolomide).

total of 12 patients will be recruited. The participants will be at least 18 years old, and will not be pregnant or lactating. Subjects with safety contraindications to MRI examination and those with hemodialysis or acute/chronic renal failure will be excluded. The participants, however, will not be excluded on the basis of race, ethnicity or sex.

The data reproducibility across two different scanners assesses between-scanner variability combined with the inaccuracy of region of interest (ROI), arterial input function (AIF) and image co-registration. The tumor ROI will be determined by [name] (a neuro-radiologist; co-I) (see "ROI determination" section for the details). The ROIs of two scans of each subject will be matched as closely as possible to minimize intra-observer variation. We recently introduced a novel method to reliably measure individualized AIFs (36) which will be employed in this study. If the patient moves during imaging, a similarity transformation (37) will be used for 3D coregistration. The pharmacokinetic (PK) parameters (e.g., K^{trans}) within the ROI will be averaged at each scan after P4-based error correction, and the mean values of two scans will be compared to calculate the reproducibility coefficient (%RDC) using the equation, %RDC=2.77wCV, where wCV is the within-subject coefficient of variation (38). The %RDC before P4-based error correction will also be calculated for comparison. Data reproducibility will be assessed using the intra-class correlation coefficient (ICC) as well. $ICC = \sigma^2 b / (\sigma^2 b + \sigma^2 w)$, where σb is between-subject standard deviation and σw is within-subject standard deviation.

Each tumor will be classified into pseudo- or true-progression based on the histopathologic data or RANO criteria. We expect approximately 40-50% of glioblastoma will be classified to

pseudo-progression, as demonstrated in previous studies (11-13). All PK parameter maps will be created within a month after image acquisition so that the image processing will not be biased by subsequent clinical findings. We will examine whether the difference of tumor PK parameters between pseudo- and true-progressions will become more statistically significant after P4-based error correction.

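### The one-month limit on PK maps fixes elapsed time, not order of events, so an early histology result can be known during image processing with the rule still met

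*Combined protocol and SAP*

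**What the plan says.** All of the relevant design text is in Section 3.1 (Study Design).

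- **Safeguard.** "All PK parameter maps will be created within a month after image acquisition so that the image processing will not be biased". The source of bias named there is what is learned clinically at a later date. The deadline is attached to the maps. No deadline is expressly attached to the tumour ROI.
- **ROI.** It is set by one reader ("a neuro-radiologist; co-I"), and the text points to an ROI determination "section for the details". That section is not in the text available for this review.
- **Who is enrolled.** Patients with a new or enlarged enhancing lesion when "it is uncertain whether it is pseudo or true-progression".
- **Reference standard.** The class "will be determined via histopathologic analysis after biopsy (or surgery") or by RANO. No interval is given between the study scans and the biopsy, the operation or the pathology report.
- **Follow-up imaging.** "standard-of-care brain MRI will be applied every 2~3 months".
- **Study scans.** Two, within one week, at least 24 hours apart.

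The flow chart ("Fig. 5. Overall study plan") is not shown in the available text. Section 8.0 compares PK parameters between the two classes with a two-group t-test. It calls the test one-sided in the sample-size text only.

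**The concern.** The rule has a stated purpose: processing should not be influenced by what is learned later about the patient. An upper limit on elapsed time achieves that only if the reference result always arrives after the processing is done. For histology, nothing in the available text ensures this. Enrolment takes place while the diagnosis is open, which is when a biopsy or operation may be considered.

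The value analysed is the average of a PK parameter within an ROI drawn by a reader, and that is the step where judgement enters most. If the reader already knows the histology, choices at the lesion margin could drift towards the expected value: higher Ktrans for true progression, lower for pseudo-progression. The group difference would then be overstated, and the t-test would reject a true null more often than its nominal level.

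**Working it through.** **Step 1. Time windows** (inputs from Section 3.1; a month taken as 28 to 31 days)

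- Maps are allowed up to day 28–31 after a scan. If the second scan is on day 7, that is up to day 7 + 28 = 35 to 7 + 31 = 38 after the first.
- Histology: no earliest date, so a report on any day from 0 to about 31 after the scan is compatible with the rule.
- RANO at the next routine MRI: 2 × 28 = 56 to 3 × 31 = 93 days after the MRI that triggered enrolment. This falls after the map limit when the last study scan is within about one month of the triggering MRI (2 months − 1 month). The documents do not give that delay, so the statement is usually true, not always.

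The gap is therefore mainly early histology.

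**Step 2. Reproduce the plan's figure** (Section 8.0: 0.44 ± 0.25 against 0.23 ± 0.10, 6 per group)

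- Pooled SD = √((0.25² + 0.10²)/2) = 0.190.
- Noncentrality = 0.21 / (0.190 × √(2/6)) = 1.91, with 10 df.
- One-sided 5% power = 0.553, which matches the stated 55%.

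**Step 3. Illustration of the harm.** The documents give neither the size of any reader-induced shift nor the number exposed; both are assumed. Take no true difference, common mean (0.44 + 0.23)/2 = 0.335, and SD 0.190 (57% of the mean). Exposure separates the groups by 10% or 20% of the mean in exposed patients. With k of 6 per group exposed, the mean shift is s × k/6, and the noncentrality is 0.335 × s × (k/6) / (0.190 × √(2/6)).

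| Exposed per group | Shift s | Noncentrality | Two-sided rejection | One-sided rejection |
|---|---|---|---|---|
| 0 of 6 | any | 0 | 5.0% | 5.0% |
| 1 of 6 | 10% / 20% | 0.05 / 0.10 | 5.0% / 5.1% | 5.5% / 6.1% |
| 3 of 6 | 10% / 20% | 0.15 / 0.30 | 5.2% / 5.9% | 6.6% / 8.7% |
| 6 of 6 | 10% / 20% | 0.30 / 0.61 | 5.9% / 8.6% | 8.7% / 14.1% |

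The last row is an outer bound. It would need early histology in every patient. Simulating exposed and unexposed patients mixed within a group, at 3 of 6, gave 5.2% / 5.7% two-sided and 6.6% / 8.5% one-sided, so the approximation is adequate.

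**Step 4. Effect on the P4 comparison.** Section 1.0 reports a fall in wCV from about 20% to about 4%. Assume that this carries over to tumours and that only the measurement part of the variance changes:

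- True-progression SD: √(0.25² − (0.20 × 0.44)² + (0.04 × 0.44)²) = 0.235.
- Pseudo-progression SD: √(0.10² − (0.20 × 0.23)² + (0.04 × 0.23)²) = 0.089.
- AUC = Φ(difference of means / √(sum of the two variances)).
- No shift (difference 0.21): 0.782 before and 0.799 after correction, a gain of 0.016 from unrounded values.
- Group means moved +10% and −10% (0.484 − 0.207 = 0.277): 0.848 before and 0.865 after, a gain of 0.017.

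The absolute AUC rises by about 0.07. The gain from correction hardly moves.

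**Step 5. Cost of leaving cases out.** If 3 of 12 are dropped, one-sided power at the Section 8.0 values and the pooled SD falls from 55% to 44% (4 against 5 left) or 41% (3 against 6 left).

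**The case against.** The case on the other side has four parts.

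- **RANO may be the main route.** Section 3.2 names RANO-based response as the primary endpoint, and the one-month limit mostly covers that route. This narrows the exposure. It does not remove it, because Section 3.1 keeps histology as a route to the label.
- **A rule may exist elsewhere.** The ROI determination section or Fig. 5 may hold a timing or masking rule. That stands: their absence here is not a fault of the plan, and ROI practice cannot be judged without them. The map deadline itself can be judged, and it does not fix order.
- **Much of the processing is algorithmic.** The phantom is segmented automatically, the arterial input follows a published method, and motion is handled by a defined transformation. This limits the bias that can enter through map creation alone and leaves the ROI as the main route.
- **It is a 12-patient pilot and the harm is assumed.** Also true. With 1 to 3 of 6 exposed per group, two-sided inflation is under one percentage point.

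Two stronger readings are tempting. A reader might infer that the primary goal, the gain from P4 correction, is biased. The documents do not support that: the same patients are compared before and after correction, and the parameter is averaged within the tumour ROI in both, so a reader-induced shift is largely common to the two. One-sided rejection under full exposure would climb noticeably with correction (from 9.3% to 11.8% at a 10% shift, from 15.9% to 23.5% at 20%) only if the SD fell from 50% to 35% of the mean, which Section 8.0 offers as a condition. A reader might also infer that results will in fact be known during processing. No biopsy timing is given from which to say so.

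**Conclusion.** The point holds as a gap between a rule and its stated aim. The one-month limit can be met in full while the histology result is known to the person drawing the ROI or making the maps. How many of the 12 patients this touches cannot be derived from the documents, and it may be none.

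The analysis at risk is mainly the absolute comparison of pseudo- and true-progression. The numerical size is illustrative only: it rests on assumed shifts of 10% to 20% of the mean, assumed exposure of 1 to 3 of 6 per group, the Section 8.0 SDs and normal data. Two-sided rejection is then 5.0% to 5.9%, and one-sided 5.5% to 8.7%. The change is worth making because it is cheap and must be set in advance: who knew what, and when, cannot be reliably reconstructed afterwards.

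**What to change.** In Section 3.1, replace the time-only rule with an order-of-events rule:

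1. After the second scan, the ROIs, PK maps and mean Ktrans (corrected and uncorrected, from the same ROI) are finalised and locked with a date. This happens before the ROI reader and the map maker have access to that patient's histology or follow-up RANO classification. One month stays as the outer limit.
2. Any case in which either person knew the result before lock is recorded, and the number is reported. An analysis without those cases is descriptive only, because it selects patients by reference-standard route and loses the power shown in Step 5.
3. If the ROI determination section or Fig. 5 already contains such a rule, cite it here instead.

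Cost: protocol wording, a dated lock file and one flag per patient. No extra patients, scans or readers are needed. The downside is that some cases must be read sooner than one month.

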8.0 STATISTICAL METHOD

> Sample Size Justification

Aim 1. The K^{trans} reproducibility measured by the ICC was 0.99 in our previous experiment ($\underline{1}$), when the P4 was used for error correction (3 volunteers x 4 tissues = 12 measurements) (see **Fig. 3C**). For brain DCE-MRI, however, the perfusion value can only be assessed in the tumor region. Thus, to achieve greater than 90% power to confirm that the data repeatability measured by the ICC is larger than 0.9 with 5% type I error, at least 12 volunteers will be needed.

Aim 2. In Yun et al's study (13), the difference of tumor K^{trans} between pseudo- and true-progressions was 91% with the standard deviation (SD) of approximately 50% in each group (p=0.004). If the mean and SD of each group in the proposed study will be the same with those of Yun et al's study (0.44±0.25 vs 0.23±0.10 min⁻¹), the sample size (n=12) will have 55% power at a 5% significant level to differentiate the two groups (assuming n=6 per group) using a one-side two-group student t-test. However, if the SD is reduced to ≤35% using the P4, the power will be increased to ≥90%.

> Statistical Analysis

Descriptive analysis with the mean and SD will be presented for each experimental parameter and each time point. Graphic presentation will be considered when appropriate. Due to repeated measurement, ANOVA analysis with a mixed model will be used to estimate the measurement error (within error) with two-sided 95% confidence interval (49). Data

reproducibility will be assessed using both the ICC and %RDC (33). Tumor PK parameters between pseudo- and true-progressions will be compared using two-group student t-test (50). Data will be transformed using natural logarithms if the variability is found to be dependent upon its mean value. All data will be analyzed using SAS (SAS institute, Cary, NC) by [name] (see her support letter).

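### The primary before/after question on P4 would be answered by comparing two p-values from the same 12 patients, with no interval planned for the change in differentiation

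*Combined protocol and SAP*

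**What the plan says.** Section 2.1 sets the primary goal: to find out "whether the differentiation between pseudo- and true-progressions of glioblastoma can be improved in quantitative DCE-MRI measurement" when the phantom is used for correction. For that goal, section 3.1 gives one before/after statement: "We will examine whether the difference of tumor PK parameters between pseudo- and true-progressions will become more statistically significant after P4-based error correction".

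Section 8.0 (Statistical Analysis) gives the tools:
- "Tumor PK parameters between pseudo- and true-progressions will be compared using two-group student t-test"
- "Descriptive analysis with the mean and SD will be presented for each experimental parameter and each time point"
- "Data will be transformed using natural logarithms if the variability is found to be dependent upon its mean value"

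The other places that might have filled the gap do not:
- The one planned 95% interval (section 8.0) is for within-subject measurement error.
- The before/after %RDC comparison (section 3.1) concerns reproducibility, which is the secondary goal (section 2.2).
- AUC appears only in a hypothetical illustration in section 1.0.
- The primary endpoint in section 3.2 is the RANO assessment. It classifies the tumours and does not measure improvement.
- The two powers under Aim 2, 55% and at least 90%, each describe one comparison of the two groups. Neither describes the change between them.

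Section 1.0 states what the pilot is for: to "conduct the preliminary test of this hypothesis before validating our methodology in an extended multi-site clinical trial".

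**The concern.** Whether P4 improves differentiation is a question about a change within the same patients. A drop in the p-value shows the direction of that change in this sample but not how precisely it is known. The uncorrected and corrected values share the same tumours and scans, so the precision of the change depends on how they vary together within patients. Group means, SDs and p-values do not carry that information.

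The plan states no success rule. Even so, the section 3.1 sentence invites a smaller corrected p-value to be read as improvement, and the multi-site trial would be planned on that reading. Its planners need to know how large the gain is and how uncertain.

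**Working it through.** **1. The plan's own figure.** Aim 2 inputs (section 8.0): means 0.44 and 0.23, SDs 0.25 and 0.10, 6 per group, one-sided 5%.
- Difference = 0.44 − 0.23 = 0.21. SE = √(0.25²/6 + 0.10²/6) = 0.110. Noncentrality = 0.21/0.110 = 1.91.
- With 10 df the critical value is 1.812 and the power is 55.3%. The stated 55% is reproduced.
- With SD at 35% of each group's own mean (0.154 and 0.0805), SE = 0.0709, noncentrality = 2.96 and power = 86.6%. The normal approximation gives 90.6%, so the stated ≥90% is roughly reproduced, depending on the method and the reading of 35%.

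**2. What the planned outputs do give.** For known group sizes, t = d·√(n₁n₂/(n₁+n₂)). With 6 and 6, d = t·√(1/6 + 1/6) = 0.577t. A one-sided p-value fixes t, and so fixes d. The means and SDs give d directly. The before/after change in d is therefore recoverable as a point estimate.

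**3. How informative the p-value ordering is.** Assumptions, for illustration only:
- Normal data, 6 per group, Aim 2 means and SDs, one-sided Student t-test, one scan per patient unless stated.
- The uncorrected SDs contain a measurement error of 20% of the mean. The 20% and 4% are within-subject CVs from organs of three volunteers (section 1.0). The documents give no glioblastoma value.
- Before and after errors are independent unless stated. In the SD 35% case, the corrected value is a component of the uncorrected one.
- At least 40,000 simulated trials per setting. Simulated uncorrected power is 56%.

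| Setting | Corrected p smaller | Non-significant to significant |
|---|---|---|
| No gain (20% to 20%) | 50% | 9% |
| Error 20% to 4% | 62% | 9% |
| Error rises to 25% | 46% | 9% |
| SD falls to 35% of each mean | 82% | 33% |

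**4. Sensitivity.**
- *Error correlation, no gain.* Correlations of 0, 0.5, 0.8 and 0.95 between before and after errors give moves to significance of 9%, 6%, 4% and 2%. The 50% does not move: errors of equal size before and after are interchangeable.
- *Error correlation, 20% to 4%.* The corrected p is smaller in 61 to 64% of trials.
- *Two scans averaged, independent errors.* With no gain, moves to significance fall to about 6 to 7%. For 20% to 4%, the corrected p is smaller in 58%.
- *Starting error, falling to 4%.* From 10%, 20%, 30% and 40%, the corrected p is smaller in about 54%, 61%, 70% and 81%.

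**5. What a paired interval would show.** Take the change in the small-sample-corrected d, where the factor with 12 patients is 1 − 3/(4·10 − 1) = 0.923. Leave out one patient at a time within group, and use a t distribution on 10 df. One scan per patient, independent errors:

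| Setting | Median 95% width | Lower limit above zero |
|---|---|---|
| No gain | 1.8 | 2% |
| 20% to 4% | 1.35 | 4% |
| SD 35% | 3.0 | 11% |

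Averaging two scans brings the 20% to 4% row to a width of about 1.0, with the lower limit above zero in about 3%. An interval built from group means and SDs alone, ignoring the pairing, has median widths of 3.43, 3.44 and 3.59. In the 20% to 4% case pairing shortens the interval by 1 − 1.35/3.44 = 61%.

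True changes in d, before the small-sample factor: d is 0.21/0.190 = 1.10 uncorrected. It is 0.21/0.178 = 1.18 after 20% to 4% (a change of 0.08) and 0.21/0.123 = 1.71 at SD 35% (a change of 0.61).

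**The case against.** The strongest reply is that the proposed estimate answers yes or no exactly as the p-values do. In every simulated trial the sign of the change in d matched the p-value ordering. With SD at 35%, where a real gain exists, the ordering is right in 82% of trials, while the interval excludes zero on the positive side in only 11%. This stands. The interval is no better detector, and its frequent inclusion of zero should not be held against the p-value as an error.

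A second reply is that this is a 12-patient pilot that only promises to examine the question. That is fair as to severity. But a preliminary test that feeds a larger trial should report an estimate with its uncertainty.

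Third, the Aim 2 justification of 12 patients rests on the t-test, so demoting that test would leave the sample size without a rationale. This also stands, and the fix keeps the t-tests.

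Three stronger readings are tempting but unsupported:
- A reader might infer that two p-values reveal nothing about the size of the change. At known group sizes they do give it; only its uncertainty is missing.
- A reader might infer a 9% chance of a spurious move to significance. That figure needs independent errors and a single scan. Section 3.1 lists ROI, AIF and co-registration as sources of inaccuracy; if they affect the uncorrected and corrected values alike, the errors are correlated and the figure is lower.
- A reader might infer that the log rule will be applied on one side only. Section 8.0 states one rule for the data and nothing says it would be applied differently. Fixing the same scale before and after is a precaution.

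**Conclusion.** The gap is real but narrow: no interval is planned for the before/after change that the primary goal asks about, and nothing else in the document supplies one. Followed as written, the plan would rest its primary answer on the ordering of two p-values.

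The firmest figure is the 50% chance of a smaller corrected p-value when P4 gives no gain. Given equally variable before and after errors, it follows from symmetry and holds at every error correlation and starting error tried. The 62% (58% with two scans averaged) and 82% figures rest on normal data, 6 per group, the Aim 2 inputs and, for the first, error sizes borrowed from volunteer organs. The documents do not support saying that the plan contains a faulty decision rule or that its power figures are wrong. This is a reporting gap on the primary goal, and it should be closed before the data are seen.

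**What to change.** Replace the section 3.1 sentence and add to section 8.0:

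> Improvement in differentiation will be reported as the paired change (corrected minus uncorrected) in the small-sample-corrected standardised mean difference of tumour Ktrans between progression groups. Each patient contributes the mean of the two scans, or the single scan if only one is available. The same scans and the same transformation are used before and after. The 95% CI is obtained by leaving out one patient at a time within group, keeping each patient's corrected and uncorrected values together, with a t distribution on the number of patients minus 2 degrees of freedom. If a group has fewer than three patients, only point estimates are given. The planned t-tests for Ktrans and the other PK parameters are kept, but improvement is not claimed from comparing their before and after p-values.

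Add to Aim 2 that the 55% and ≥90% powers each refer to a single group comparison, and that the change is estimated, not powered. Ktrans is named because Aim 2 is built on it.

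Cost: wording and a short program on data already planned.

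Downside: the interval is wide with 12 patients, and its lower limit will rarely exceed zero even if P4 works. In one-scan simulations its coverage was 94 to 96% with 6 per group and normal data, and about 92 to 94% on the raw scale with only 4 true progressions. If 40 to 50% of tumours are pseudo-progression, as section 3.1 expects, a group of two or fewer occurs in about 4 to 9% of such studies (binomial, 12 patients), and then no interval is given.
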